14.3.4.1. Primary Utilization Variable and Analysis

The primary utilization analysis will be performed on the ITT population at Day 1 and will present the ease of intravitreal administration reported by Investigators, including the satisfactory ratings proportion, for the Mk I inserter and the Mk II inserter groups of eyes employing descriptive statistics including 95% confidence intervals using the exact binomial methodology.

The primary utilization analysis will be conducted after all eyes in the study have completed study Day 7 or have discontinued study participation.

The trial will be deemed a success for the Mk II inserter if the following condition is met:

The proportion of Mk II procedures scored as satisfactory (i.e., VE, E or R) is not numerically lower than the corresponding proportion of Mk I procedures.

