3.1. Overall Study Design and Plan

This trial is a 12 month, phase 3, multi-center, randomized, single-masked (subject), controlled study designed to evaluate the utilization and safety of the Mk II inserter and the safety of the FAI insert, in subjects with non-infectious uveitis affecting the posterior segment of the eye. This study will be conducted in at least 3 study sites. Enrollment of approximately 25 subjects is expected. A total enrollment of approximately 30 eyes is planned for this study (20 Mk II inserter: 10 Mk I inserter) in one or both eyes in each subject.

All subjects will receive the FAI insert on Day 1 of the study, administered using either an Mk I inserter or an Mk II inserter. If both eyes in a subject with bilateral uveitis satisfy the study's inclusion/exclusion criteria, both eyes may be enrolled in the study. In this case, randomization of a subject's second eye will occur independently and will occur no earlier than the study Day 7 visit for the subject's first study eye.

At least 10 different investigators will administer the FAI insert. Each time a subject's eye is enrolled in the study, one investigator will serve as the treating investigator (Investigator); another staff member in the study site will serve as the trained observer (Observer). On study Day 1, the Investigator will administer the FAI insert, and the Observer will observe the procedure used by the Investigator to administer the FAI insert. The Investigator and the Observer will complete questionnaires related to the administration of the FAI insert on Day 1. The Investigator (or designee) will perform all subsequent study assessments. Study personnel will not disclose to the subject which inserter was used for intravitreal administration of the FAI insert.

Subjects will receive standard care in the study eye(s) and any non-study eye for 12 months following enrollment, in accord with medical need and the Investigator's standard practice. Eyes will be assessed according to the schedule of procedures and assessments (Appendix 13.1).

Analyses of study data will be performed at the following two time points during the study:

- 1. After all subjects have completed the Day 7 visit (or have been discontinued from the study prior to this visit). The primary utilization and safety analyses of the inserters will be conducted at Day 7 time point.

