4.1. Sample Size

This study is not statistically powered to detect a difference between the Mk I and Mk II inserters for the proportion of satisfactory procedures.

With a sample size of 20 eyes in the Mk II inserter group, the 95%, two-sided confidence interval of satisfactory procedures in the Mk II inserter group will be no larger than 27.2% - 72.8% when the exact binomial method and a proportion of 10 satisfactory procedures out of 20 Mk II inserter procedures are employed. All other satisfactory procedure proportions for the Mk II inserter will result in two-sided, 95% confidence bounds that are narrower than that described above.

With a sample size of 10 eyes in the Mk I inserter group, the 95%, two-sided confidence interval of the satisfactory procedures proportion will be no larger than 18.7% - 81.3% when the exact binomial method and a satisfactory procedures proportion of 5 out of 10 are employed. All other satisfactory procedures proportions for the Mk I inserter will result in two-sided, 95% confidence bounds that are narrower than that described above.

These confidence bounds, based on eye, are thought to adequately characterize the ease of use and other performance characteristics of the two inserters being studied.

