8.1. Primary Utilization Endpoint

The primary utilization endpoint is defined as the proportion of intravitreal insertion procedures that are assessed by the Investigator as satisfactory. A satisfactory procedure is defined as one receiving a score from the Investigator as either Very Easy (VE), Easy (E), or Routine (R), according to the following categories:

- Very Easy (VE)
- Easy (E)
- Routine (R)
- Difficult (D)
- Very Difficult (VD)

If more than one inserter is used for the same eye, the results from the first inserter will be used for completing the questionnaires and analysis. Comments related to the second inserter will be presented in a listing. Any injector which penetrates the eye but does not deliver the FAI insert into the eye will be scored as Very Difficult for analysis.

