8.1.1. Primary Utilization Analysis

The primary utilization analysis will compare the proportion of intravitreal insertion procedures that are assessed by the Investigator as satisfactory (i.e., VE, E or R), in the Mk I inserter and the Mk II inserter groups.

The number and percentage of eyes with satisfactory intravitreal insertion procedures will be presented, for the Mk I inserter and the Mk II inserter groups of eyes employing descriptive statistics including 95% confidence intervals using the exact binomial methodology. The difference in proportions, the 95% exact unconditional confidence interval for the treatment difference (Mk II vs Mk I) in proportions, and the Fisher's exact test p-value will also be provided, however this comparison is considered exploratory only as the study is not powered to detect a difference between the inserters.

The primary utilization analysis will be conducted after all eyes in the study have completed study Day 7 or have discontinued study participation.

The study will be deemed a success for the Mk II inserter if the following condition is met: The proportion of Mk II procedures scored as satisfactory is not numerically lower than the corresponding proportion of Mk I procedures.

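### The success verdict for Mk II rests on the sign of a difference that the SAP itself calls exploratory; with 20 v 10 eyes, equal inserters would miss it in about 41-45% of trials at common true rates of 50-95%

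*SAP*

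**What the plan says.** Each procedure is rated by the Investigator who performed it on a five-point ease scale, and the top three ratings, down to Routine, count as satisfactory (SAP 8.1; Protocol 13.1).

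Protocol 14.3.4.1 introduces the decision rule with "The trial will be deemed a success for the Mk II inserter if the following condition is met", and the condition is that the Mk II proportion "is not numerically lower than the corresponding proportion of Mk I procedures". SAP 8.1.1 has the same rule. The protocol Synopsis, under Statistical Methods, also has it, but without the qualifier that the comparison is numerical. A tie counts as success. No margin, confidence limit or assumed rate enters the rule.

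SAP 8.1.1 also plans the difference in proportions with an exact unconditional 95% interval and a Fisher p-value, adding that "this comparison is considered exploratory only as the study is not powered to detect a difference between the inserters". SAP 4.1 opens with "This study is not statistically powered to detect a difference between the Mk I and Mk II inserters". The sample size of 20 Mk II and 10 Mk I eyes is justified only by the widest possible single-arm intervals. Neither document says how often the success rule would be met under any assumed pair of rates.

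**The concern.** The plan disclaims the comparison between inserters and then takes its one formal verdict from the sign of that comparison. The interval that would show how uncertain the difference is plays no part in the verdict.

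With 20 and 10 eyes, a single rating can decide the outcome. If Mk I scores 10/10, one Difficult rating among 20 Mk II procedures turns success into non-success. The label may then be read as evidence in either direction, although the data behind it would barely distinguish the inserters. A non-success would also attach to a device that Protocol 5.3 expects to be easier to use.

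**Working it through.** **1. The plan's own figures.** The exact (Clopper-Pearson) limits for x of n are the 2.5% quantile of Beta(x, n−x+1) and the 97.5% quantile of Beta(x+1, n−x).

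- 10/20: Beta(10, 11) and Beta(11, 10) give 27.2% and 72.8%, as SAP 4.1 states ("will be no larger than 27.2% - 72.8% when the exact binomial method and a proportion of 10 satisfactory procedures out of 20").
- 5/10: Beta(5, 6) and Beta(6, 5) give 18.7% and 81.3%, as stated ("will be no larger than 18.7% - 81.3% when the exact binomial method and a satisfactory procedures proportion of 5 out of 10").

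Both reproduce, and both are the widest intervals at their sample size. They describe each arm alone and say nothing about the success rule.

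**2. The success rule.** Inputs from the documents: 20 Mk II and 10 Mk I eyes, a binary rating per eye, and a tie counting as success. Inputs assumed here: the true rates p2 (Mk II) and p1 (Mk I), and independent eyes. With X2 ~ Bin(20, p2) and X1 ~ Bin(10, p1), success means X2/20 ≥ X1/10, that is X2 ≥ 2·X1. So

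P(success) = Σ over y = 0..10 of P(X1 = y) × P(X2 ≥ 2y).

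**3. Worked case, p1 = p2 = 90%.**

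| Mk I result | P(X1 = y) | P(X2 ≥ 2y) | Contribution to missing the rule |
|---|---|---|---|
| 10/10 | 0.3487 | 0.1216 | 0.3487 × 0.8784 = 0.3063 |
| 9/10 | 0.3874 | 0.6769 | 0.3874 × 0.3231 = 0.1252 |
| 8/10 | 0.1937 | 0.9568 | 0.1937 × 0.0432 = 0.0084 |
| 7/10 | 0.0574 | 0.9976 | 0.0574 × 0.0024 = 0.0001 |
| Total | | | 0.440 |

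Most of the risk comes from Mk I scoring 10/10, after which Mk II must score 20/20.

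**4. Equal inserters, probability of missing the rule (20 v 10).**

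| Common true rate | 50% | 60% | 70% | 80% | 90% | 95% | 97% | 98% | 99% |
|---|---|---|---|---|---|---|---|---|---|
| P(miss) | 0.449 | 0.452 | 0.452 | 0.449 | 0.440 | 0.408 | 0.341 | 0.273 | 0.165 |

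Above 95%, ties at 10/10 and 20/20 become common and the figure falls.

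**5. Unequal inserters (20 v 10).**

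| Mk II v Mk I | P(success) | P(miss) |
|---|---|---|
| 80 v 90 | 0.271 | 0.729 |
| 85 v 95 | 0.224 | 0.776 |
| 70 v 90 | 0.106 | 0.894 |
| 95 v 90 | 0.747 | 0.253 |
| 90 v 80 | 0.805 | 0.195 |

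**6. Sensitivity to the split.** Protocol 7.2 sets 20 and 10 as minimum numbers, so the final split may differ. The same sum, with success defined as X2/n2 ≥ X1/n1, gives these probabilities that equal inserters miss the rule:

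- 19 v 10: 0.551 at 80% and 0.549 at 90%.
- 20 v 11: 0.526 at 80% and 0.538 at 90%.

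At these splits exact ties nearly disappear, so a change of one eye moves the figure by about 8 to 11 points.

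**7. One rating, two verdicts.** Mk I 10/10 with Mk II 19/20 is a non-success. With one unsatisfactory rating among 30 eyes, it falls in the Mk II arm with probability 20/30 and in the Mk I arm with probability 10/30. The observed table is the more likely one, so the two-sided Fisher p-value is 20/30 + 10/30 = 1.0. Mk I 10/10 with Mk II 20/20 is a success, yet the exact unconditional 95% interval for the difference is about −38 to +38 points. That interval inverts the raw difference; the SAP does not name a statistic.

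**The case against.** The strongest reply is that the study is openly descriptive. The SAP says that it is unpowered and that the comparison is exploratory, Protocol 14.3.4 says all utilization analyses are descriptive, and the rule in 14.3.4.1 and SAP 8.1.1 says the comparison is numerical. The arm-specific exact intervals are already in the primary analysis, and the interval for the difference is already in the SAP. All of this stands. It limits the point to the verdict and does not dispose of it, because a descriptive study needs no pass/fail rule and this one has one.

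Three stronger readings are tempting, and the documents do not support them.

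- *The sponsor plans to claim comparability or non-inferiority.* Neither document makes or plans such a claim. The risk lies in how a success label may be read.
- *Equal inserters fail 40-45% of the time, whatever the rate.* The documents state no rate. Because Routine counts as satisfactory, rates above 95% are possible, and there the figure falls to 34% (97%) and 17% (99%).
- *A clearly worse Mk II would probably pass.* It can pass, but usually would not: the two 10-point deficits above fail in 73-78% of trials, and the 20-point deficit in 89%.

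The calculation also ignores correlation. About 30 eyes are expected from about 25 subjects, and at least 10 investigators rate their own procedures. The documents give nothing from which to size that effect.

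**Conclusion.** The point holds for the success verdict, not for the study's descriptive aims. Followed as written, the rule comes close to a coin flip for inserters that are truly alike, over a wide range of rates, and it misses a modestly better Mk II in about a quarter of trials. A success would not show that Mk II is comparable, and a non-success would not show that it is worse.

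The figures rest on assumed true rates, independent eyes and a split of exactly 20 v 10. They fall when nearly all procedures are satisfactory, and they rise to about 53-55% at common rates of 80% and 90% if the split is 19 v 10 or 20 v 11. None of these conditions makes the sign of the difference an informative verdict. The matter deserves correction because it governs the headline conclusion and the remedy is cheap.

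**What to change.** Change all three statements of the rule together: protocol Synopsis, Protocol 14.3.4.1 and SAP 8.1.1. Editing only some of them would leave the documents in conflict.

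- Replace the success verdict with a descriptive primary result: the two satisfactory proportions with exact 95% intervals, and the difference (Mk II minus Mk I) with the exact unconditional 95% interval that SAP 8.1.1 already plans. The protocol does not yet mention the interval for the difference and should.
- Add a sentence saying that the direction of the observed difference alone supports no conclusion that Mk II is comparable, better or worse.
- If the sponsor keeps the numerical criterion, label it descriptive and report it only alongside that interval. Give its operating characteristics in SAP 4.1, stating the assumed rates, independence and split.

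No margin, extra eyes or new analysis is needed. The costs are the loss of a headline success label and a wording amendment to the protocol, which under Protocol 9.17 may need IRB/EC and regulatory approval if it is treated as a significant change.

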8.2. Secondary Utilization Endpoints and Analysis

Secondary endpoints include:

- Clarity of the instructions for use, as assessed by the Investigator (yes, no)
- Differences between observed procedure and instructions for use, as assessed by an Observer (yes, no)

These secondary utilization endpoints will be analyzed employing descriptive statistics. Additionally descriptive statistics for other items on the investigator and observer questionnaires will be presented.

9. Safety Analysis

Safety analyses will be performed by treatment group for the Safety population at Day 7 and Month 12. Descriptive statistics will be used in safety analyses. Summary at the subject level will also be provided.

Non-treated randomized eyes and non-study eyes will only have all safety data listed. Adverse events will be summarized for these eyes, but otherwise they will not be included in safety tabulations.

9.1. Adverse Events

A treatment-emergent AE (TEAE) is defined as any new untoward medical occurrence or worsening of a pre-existing medical condition in a subject administered an investigational product; an AE does not necessarily have a causal relationship with this treatment. An AE can therefore be any unfavorable and unintended sign (including an abnormal laboratory finding, for example), symptom, or disease temporally associated with the use of investigational product, whether or not considered related to the investigational product.

For the purpose of inclusion in TEAE tables, incomplete AE start and end dates will be imputed as follows:

Missing onset dates (where UK and UKN indicate unknown or missing day and month respectively):

• UK-MMM-YYYY: If the month and year are different from the month and year of the date of injection, assume 01-MMM-YYYY. If the month and year are the same as the month and year for the date of injection, and the end date (after any imputation) is on or after the date of injection, then assume the date of injection (Day 1). If the month and year are the same as the date of injection, and the end date (after any imputation) is prior to the date of injection, then assume the end date for the start date.

• DD-UKN-YYYY/UK-UKN-YYYY: If the year is different from the year of the date of injection, assume 01-JAN-YYYY of the collected year. If the year is the same as the date of injection year, and the end date (after any imputation) is on or after the date of injection, then assume the date of injection (Day 1). If the year is the same as the date of injection, and the end date (after any imputation) is prior to the date of injection, then assume the start date.

Missing end dates (where UK and UKN indicate unknown or missing day and month respectively):

- UK-MMM-YYYY: Assume the last day of the month;
- DD-UKN-YYYY/UK-UKN-YYYY: Assume 31-DEC-YYYY.

All adverse events will be classified by System Organ Class (SOC) and Preferred Term (PT) according to the Medical Dictionary for Regulatory Activities (MedDRA, Version 15.1 or higher).

An overview summary of any TEAE, serious TEAE, treatment-related TEAE, treatment-related serious TEAE, TEAE leading to FAI insert removal, TEAE leading to study discontinuation, and AE leading to death will be provided.

All TEAE summaries will be provided for ocular events and non-ocular events, separately. All adverse events starting on or after the date of treatment in the first study eye are considered TEAE, however ocular events occurring in non-treated eyes and events occurring in the second treated eye between the date of treatment in the first treated eye and the date of treatment in the second treated eye will be summarized separately from ocular events that occur in treated eyes after the date of treatment within the respective eye.

All AEs will be presented in a listing.

9.1.1. Incidence of Adverse Events

Summaries of the total number of ocular TEAEs and the number and percentage of eyes having at least one ocular TEAE will be provided by treatment group and for all treated eyes. Similarly, summaries of the total number of non-ocular TEAEs and the number and percentage of subjects having at least one non-ocular TEAE will be provided by treatment group. Ocular events and non-ocular events will be also summarized at the subject level for all subjects. Ocular events which occur in non-treated eyes and ocular events which occur in the second treated eye with a start date on or after the date of treatment in the first study eye but before the date of treatment in the second eye will be summarized separately as noted in section 9.1.10.

Ocular and non-ocular TEAEs will be summarized by SOC and PT. At each level of summarization, eye or subject level, an eye or subject is counted once for multiple events within PT/SOC.

Summaries by treatment group and for all treated eyes will be based on the number of treated eyes; therefore non-ocular events for subjects who have both eyes treated may be counted more

than once, "repeating" and counting the adverse event once for each treated eye. A non-ocular event will be counted for a given eye if the event start date is on or after the treatment date in the given eye. (i.e., non-ocular events which occur on or after the date of treatment in the first treated eye but before the date of treatment in the second eye will be counted once for the first eye only. If the event start date was on or after the treatment date in the second treated eye, the event would be counted twice, once for each eye.) Ocular events will be counted for a given study eye/treatment if the event start date is on or after treatment date within the given treated eye. Percentages will be calculated out of the number of treated eyes in the Safety Population.

Subject level summaries for all subjects will be based on the number of subjects who have at least one treated eye and a subject will be counted as having an event in the total subject summary if the subject has an event in at least one treated eye. Percentages will be calculated out of the number of subjects in the Safety Population with at least one treated eye.

The summary of TEAEs will be presented in descending order from the SOC with the highest subject incidence to the SOC with the lowest subject incidence. If the incidence for any two or more SOC is equal, the SOC will be presented in alphabetical order. Within each SOC, the PTs will be presented in alphabetical order.

A separate summary of protocol defined ocular TEAEs, overall and by criteria, will be provided. This summary will include the following ocular events, as reported on the AE eCRF page:

- decrease in visual acuity of \geq 15 letters, compared to the most recent previous measurement of visual acuity
- moderate or severe (grade 3 or 4) ocular findings compared to the last ophthalmic examination
- worsening of ≥ 2 steps in anterior chamber cell count or vitreous haze, compared to the last ophthalmic examination
- increase in IOP of \geq 10 mmHg at two visits at least 1 week apart or an increase in IOP to \geq 25 mmHg

9.1.2. Relationship of Adverse Events to Study Treatment

A summary of TEAEs by relationship to study treatment will be presented in a table by incidence of occurrence by treatment group. The investigator will provide an assessment of the relationship of the event to the study treatment. The possible relationships are "Unrelated", "Possibly Related", and "Probably Related". TEAEs that are missing a relationship will be presented in the summary table as "Probably Related" but will be presented in the data listing with a missing relationship.

The TEAE data will be categorized and presented by SOC, PT, and relationship in a manner similar to that described in Section 9.1.1.

9.1.3. Severity of Adverse Event

A summary of TEAEs by severity will be presented in a table by incidence of occurrence by treatment group. The severity will be captured on the eCRF page. The possible severities are "Mild," "Moderate," and "Severe." TEAEs that are missing severity will be presented in tables as "Severe" but will be presented in the data listing with a missing severity.

A summary of TEAEs related to study treatment by severity will be presented in a table. Events with a relationship if "Possibly Related" and "Probably Related" will be considered related to study treatment and included in this summary.

The TEAE data will be categorized and presented by SOC, PT, and severity in a manner similar to that described in Section 9.1.1.

9.1.4. Serious Adverse Events

Serious treatment-emergent adverse events (SAEs) as below will be presented in a table by incidence of occurrence by treatment group.

- Results in death
- Is life-threatening
- Requires in-patient hospitalization or prolongs existing hospitalization
- Results in persistent or significant disability / incapacity
- Is a congenital anomaly / birth defect
- Is a medically important event or reaction

The SAE data will be categorized and presented by SOC and PT in a manner similar to that described in Section 9.1.1 and by severity as described in Section 9.1.3.

A separate summary of protocol defined SAEs, overall and by criteria, will be provided. This summary will include the following sight-threatening ocular events, as reported on the AE/SAE eCRF page:

- An AE which causes a decrease in visual acuity of ≥ 30 letters, compared to the most recent previous measurement of visual acuity, lasting more than 1 hour
- An AE which causes a decrease in visual acuity to light perception or worse, lasting more than 1 hour
- An AE which requires surgical intervention (e.g., conventional surgery, vitreous tap or biopsy with intravitreal injection of anti-infective, or laser or retinal cryopexy with gas) to prevent permanent loss of sight
- An AE which is associated with severe intraocular inflammation (i.e., 4.0 anterior chamber cell score, 4+ flare or 4+ vitritis)
- Two consecutive IOP measurements of 30 mmHg or higher taken at least 72 hours apart when a subject is already being treated with two glaucoma medications
- An IOP < 6 mmHg requiring medical intervention
- An AE which in the opinion of the Investigator requires medical or surgical intervention to prevent permanent loss of sight

